12.4.2 Analysis of Secondary Effectiveness Endpoint

The secondary effectiveness objective is to demonstrate noninferiority [REDACTED] compared to Biofinity in the percentage of subjects achieving CLCDVA 20/20 or better, in each eye, at Week 1 Follow-up.

The corresponding endpoint is the percentage (proportion) of subjects with CLCDVA of 20/20 or better, measured monocularly, in both OD and OS at Week 1 Follow-up.

12.4.2.1 Statistical Hypotheses

The null and alternative hypotheses are formulated in terms of the predefined margin of 0.10 (10%) for noninferiority.

$$H_0: P_{(T)} - P_{(C)} \leq -0.10$$

$$H_a: P_{(T)} - P_{(C)} > -0.10$$

where $P_{(T)}$ and $P_{(C)}$ denote the proportion of subjects attaining at least 20/20 in CLCDVA at Week 1 Follow-up in each eye (OD and OS) for [REDACTED] and Biofinity contact lenses, respectively.

12.4.2.2 Analysis Methods

A binary variable will be defined for each subject to indicate whether the CLCDVA at Week 1 Follow-up is no worse than 20/20 in both OD and OS, and the corresponding proportion will be computed for each lens using the number of subjects as the denominator [REDACTED]

[REDACTED] From the two-sided 95% CI on the lens difference ([REDACTED] minus Biofinity),

noninferiority in proportion of subjects achieving 20/20 or better in CLCDVA in both eyes will be declared if the lower confidence limit is greater than -0.10.

[Redacted]

[Redacted]

[Redacted]

| [Redacted]

| [Redacted]

[Redacted]

| [Redacted]

| [Redacted]

| [Redacted]

| [Redacted]

| [Redacted]

| [Redacted]

| [Redacted]

| [Redacted]

| [Redacted]

| [Redacted]

| [Redacted]

| [Redacted]

| [Redacted]

[Redacted]

[Redacted]

[Redacted]

[Redacted]

[Redacted]

[REDACTED]

[REDACTED]

[REDACTED]

12.5 Handling of Missing Data

All data obtained in evaluable subjects/eyes will be included in the analysis. No imputation for missing values will be carried out for the primary and secondary effectiveness analyses.

Incidence and reasons for discontinuation by lens group will be tabulated at each visit and overall.

12.6 Safety Analyses

The safety endpoints are:

- AEs
- Biomicroscopy Findings
- Device Deficiencies

There are no safety hypotheses planned in this study. The focus of the safety analysis will be a comprehensive descriptive assessment of occurrence of AE as well as the other listed parameters.

All AEs occurring from the time a subject signs informed consent to study exit will be accounted for in the reporting. Safety analyses will be conducted using the safety analysis set on a treatment-emergent basis. Descriptive summaries (counts and percentages) for ocular and nonocular AEs will be presented by Medical Dictionary for Regulatory Activities Preferred Terms. AEs leading to study discontinuation, significant non-serious AEs, and SAEs will be identified. Individual subject listings will be provided, as necessary.

Individual subject listings will be provided for AEs that occur after signing informed consent but prior to exposure to IP.

[REDACTED]

Two listings for device deficiencies, prior to exposure of study contact lenses and treatment-emergent, will be provided. Additionally, each device deficiency category will be tabulated.

No inferential testing will be done for safety analysis.

[Redacted]

[Redacted]

[Redacted]

[Redacted]

[Redacted]

- | [Redacted]
- | [Redacted]

13 DATA HANDLING AND ADMINISTRATIVE REQUIREMENTS

13.1 Subject Confidentiality

The Investigator must ensure that the subject’s anonymity is maintained throughout the course of the study. In particular, the Investigator must keep an enrollment log with confidential identifying information that corresponds to the subject numbers and initials of each study participant. [Redacted]

[figure not shown]
[Redacted]

[Redacted content]

13.2 Completion of Source Documents and Case Report Forms

The nature and location of all source documents will be identified to ensure that original data required to complete the CRFs exist and are accessible for verification by the site monitor, and all discrepancies shall be appropriately documented via the query resolution process. Site monitors are appointed by the Study Sponsor and are independent of study site staff.

[Redacted content]

13.3 Data Review and Clarifications

A review of CRF data to the subject's source data will be completed by the site monitor to ensure completeness and accuracy. After the CRFs have been completed, additional data clarifications and/or additions may be needed as a result of the data cleaning process. Data clarifications are documented and are part of each subject's CRF.

13.4 Sponsor and Monitoring Responsibilities

The Study Sponsor will designate a monitor to conduct the appropriate site visits at the appropriate intervals according to the study monitoring plan. The clinical investigation will be monitored to ensure that the rights and well-being of the subjects are protected, the reported data are accurate, complete, and verifiable from the source documents, and the study is conducted in compliance with the current approved protocol (and amendments[s], if applicable), with current GCP, and with applicable regulatory requirements.

The site may not screen subjects or perform the informed consent process on any subject until it receives a notification from an appropriate Study Sponsor representative that the site may commence conducting study activities. Monitoring will be conducted periodically while the clinical study is ongoing. Monitoring methods may include site visits, telephone, written and fax correspondence. Close-out visits will take place after the last visit of the last subject at the site.

A Coordinating Investigator may be identified by the Study Sponsor to review and endorse the final study report. In cases where a Coordinating Investigator is engaged, the Study Sponsor will select the Coordinating Investigator based upon their experience, qualifications, active study participation, and their willingness and availability to take on this role.

13.5 Regulatory Documentation and Records Retention

The Investigator is required to maintain up-to-date, complete regulatory documentation as indicated by the Study Sponsor and the Investigator's files will be reviewed as part of the ongoing study monitoring. [REDACTED]

[REDACTED]

13.6 Quality Assurance and Quality Control

The Study Sponsor will secure agreement from all involved parties to ensure direct access to all study related sites, source data and documents, and reports for the purpose of monitoring and auditing by the Study Sponsor, and inspection by domestic and foreign regulatory authorities. Quality control will be applied to each stage of data handling to ensure that all data are reliable and have been processed correctly. Agreements made by the Study Sponsor with the Investigator/Institution and any other parties involved in the clinical study will be provided in writing as part of the protocol or as a separate agreement.

14 ETHICS

[REDACTED]

- I [REDACTED]
- I [REDACTED]
- I [REDACTED]

The Investigator must ensure that all personnel involved in the conduct of the study are qualified to perform their assigned responsibilities through relevant education, training, and experience. The Investigator and all clinical study staff must conduct the clinical study in compliance with the protocol. Deviations from this protocol, regulatory requirements and/or GCP must be recorded and reported to the Sponsor prior to database lock. If needed,

corrective and preventive action should be identified, implemented, and documented within the study records. Use of waivers to deviate from the clinical protocol is prohibited.

Before clinical study initiation, this protocol, the informed consent form, any other written information given to subjects, and any advertisements planned for subject recruitment must be approved by an IRB/IEC. [REDACTED]

[REDACTED]

Voluntary informed consent must be obtained in writing from every subject and the process shall be documented before any procedure specific to the clinical investigation is applied to the subject. The Investigator must have a defined process for obtaining consent. [REDACTED]

[REDACTED]

Short Title:

**Statistical Analysis Plan
CLL949-C018 / NCT04207749**

Full Title:

**Statistical Analysis Plan
CLL949-C018**

Protocol Title: Clinical Evaluation of a Daily Wear Silicone Hydrogel Lens

Project Number: [REDACTED]

Reference Number:

Protocol TDOC Number: TDOC-0056860

Author: [REDACTED]

[REDACTED]

[REDACTED]

[REDACTED]

Approvals: See last page for electronic approvals.

Job Notes:

This is the first revision (Version 2.0) of the Statistical Analysis Plan for this study. This version of the Statistical Analysis Plan is based on Version 2.0 of the study protocol.

Executive Summary:

Key Objectives:

The primary effectiveness objective is to demonstrate noninferiority of [REDACTED] soft contact lenses [REDACTED] compared to BIOFINITY® soft contact lenses (Biofinity), in contact lens corrected distance visual acuity (CLCDVA) at Week 1 Follow-up.

The secondary effectiveness objective is to demonstrate noninferiority of [REDACTED] compared to Biofinity in the percentage of subjects achieving CLCDVA 20/20 or better, in each eye, at Week 1 Follow-up.

[REDACTED]

[REDACTED]

[REDACTED]

[REDACTED]

[REDACTED]

[REDACTED]

Table of Contents

Statistical Analysis Plan CLL949-C018	1
Table of Contents	3
List of Tables.....	4
1 Study Objectives and Design.....	5
1.1 Study Objectives.....	5
1.2 Study Description.....	5
1.3 Randomization.....	6
1.4 Masking.....	6
█	█
2 Analysis Sets.....	7
2.1 Safety Analysis Set.....	7
2.2 Full Analysis Set.....	7
2.3 Per Protocol Analysis Set	7
3 Subject Characteristics and Study Conduct Summaries.....	8
4 Effectiveness Analysis Strategy.....	8
4.1 Effectiveness Endpoints	9
4.2 Effectiveness Hypotheses.....	10
4.3 Statistical Methods for Effectiveness Analyses.....	10
4.3.1 Primary Effectiveness Analyses	10
4.3.2 Secondary Effectiveness Analyses	11
█	█
█	█
█	█
█	█
5 Safety Analysis Strategy.....	13
5.1 Safety Endpoints.....	14
5.2 Safety Hypotheses	14
5.3 Statistical Methods for Safety Analyses	14
5.3.1 Adverse Events.....	14
5.3.2 Biomicroscopy Findings/Slit Lamp Examination	15

1 Study Objectives and Design

To address the primary and secondary effectiveness objectives, data from a pre-determined subset of subjects from CLL949-C009 will be combined with data from the current study, and all planned analyses will be performed on the combined set of data.

1.1 Study Objectives

PRIMARY OBJECTIVE

The primary effectiveness objective is to demonstrate noninferiority [REDACTED] compared to Biofinity in mean CLCDVA at Week 1 Follow-up.

SECONDARY OBJECTIVE

The secondary effectiveness objective is to demonstrate noninferiority [REDACTED] compared to Biofinity in the percentage of subjects achieving CLCDVA 20/20 or better, in each eye, at Week 1 Follow-up.

1.2 Study Description

Key components of the study are summarized in Table 1-1.

Table 1-1 Study Description Summary

Study Design	Prospective, multi-center, randomized, [REDACTED], controlled, double-masked, parallel-group
Study Population	Volunteer subjects aged 18 or over who are adapted daily wear frequent replacement soft contact lens wearers, excluding Biofinity habitual wearers, have at least 3 months of soft contact lens wearing experience, and who wear their habitual lenses at least 5 days per week and at least 8 hours per day. [REDACTED] [REDACTED] [REDACTED] [REDACTED] [REDACTED] [REDACTED]

	Target to complete: 192 subjects (128:64; Test:Control) [REDACTED] [REDACTED] [REDACTED] Planned: ~252 subjects enrolled, ~228 subjects randomized (152:76; Test:Control)
Number of Sites	~14-17 (US)
Test Product	[REDACTED] soft contact lenses [REDACTED]
Control Product	CooperVision® BIOFINITY® (comfilcon A) soft contact lenses (Biofinity)
Duration of Treatment	Approximately 3 months
Visits	Visit 1: Screening/Baseline/Dispense (Day 1) Visit 2: Week 1 Follow-up [REDACTED] Visit 3: Month 1 Follow-up [REDACTED] Visit 4: Month 3 Follow-up/Exit [REDACTED]

1.3 Randomization

A member of the Randomization Programming group at Alcon who is not part of the study team will generate the randomized allocation schedule(s) for study lens assignment.

[REDACTED]
[REDACTED]

Subjects will be randomized in a 2:1 ratio to receive either [REDACTED] or Biofinity contact lenses, respectively. [REDACTED]

[REDACTED]
[REDACTED]
[REDACTED]

[REDACTED]
[REDACTED]

[REDACTED]
[REDACTED]

1.4 Masking

This study is double-masked.

[REDACTED]

[REDACTED]

[REDACTED]

2 Analysis Sets

Data from a subset of subjects in the CLL949-C009 study will be combined with data from this study. This combined set will serve as the basis for all analyses for the primary and secondary effectiveness objectives. Subjects in CLL949-C009 will be included in the combined set only if they satisfy the following criterion:

- Best corrected visual acuity (BCVA) of 20/20 or better in each eye at the Screening / Baseline / Dispense Visit

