12 ANALYSIS PLAN

Data from a subset of subjects in the CLL949-C009 study will be combined with data from this study. This combined set will serve as the basis for all analyses detailed in this section. Subjects in CLL949-C009 will be included in the combined set only if they satisfy the following criterion:

- BCVA of 20/20 or better in each eye at the Screening / Baseline / Dispense Visit

[REDACTED]

[REDACTED]

[REDACTED]

[REDACTED]

[REDACTED]

[REDACTED]

[REDACTED]

[REDACTED]

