12.2 Analysis Sets

12.2.1 Safety Analysis Set

Safety analyses will be conducted using the safety analysis set on a treatment-emergent basis. As such, the safety analysis set will include all subjects/eyes exposed to any study lenses evaluated in this study, [REDACTED]

[REDACTED] For treatment-emergent safety analyses, subjects/eyes will be categorized under the actual study lenses exposed.

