2.1 Safety Analysis Set

Safety analyses will be conducted using the safety analysis set on a treatment-emergent basis. As such, the safety analysis set will include all subjects/eyes exposed to any study lenses evaluated in this study. [REDACTED]

[REDACTED] For treatment-emergent safety analyses, subjects/eyes will be categorized under the actual study lenses exposed.

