2.2 Full Analysis Set

The full analysis set (FAS) is the set of all randomized subjects who are exposed to any study lenses evaluated in this study, and who have at least one post-baseline (post-Dispense) CLCDVA. [REDACTED]

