2.3 Per Protocol Analysis Set

The per protocol (PP) analysis set is a subset of FAS and excludes all data/subjects that have met any of the critical deviation or evaluability criteria identified in the Deviations and Evaluability Plan (DEP).

3 Subject Characteristics and Study Conduct Summaries

Demographic information (age, sex, ethnicity, and race), recent lens-wearing experience (wear modality, wear success), and habitual lens information will be presented by lens group and overall for the safety, full, and per protocol analysis sets.

Baseline data will also be summarized by lens group and overall on the safety, full and per protocol analysis sets.

[REDACTED]

- [REDACTED]
- [REDACTED]
- [REDACTED]
- [REDACTED]
- [REDACTED]
- [REDACTED]
- [REDACTED]
- [REDACTED]

4 Effectiveness Analysis Strategy

[REDACTED]

[REDACTED]

[REDACTED] Primary inference will be done on the PP analysis set. [REDACTED]

[REDACTED]

[REDACTED]

[REDACTED]

[REDACTED]

[REDACTED]

[REDACTED]

[REDACTED]

[REDACTED].

All data obtained in evaluable subjects/eyes will be included in the analysis. No imputation for missing values will be carried out for the effectiveness analyses.

For all planned inferential analyses, alternative models/methods may be considered if convergence cannot be achieved.

[figure not shown]

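### Does the uneven wording on how far the pool with CLL949-C009 extends leave the safety set undefined?

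*SAP*

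**What the plan says.** Three sentences describe the reach of the pool.

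- Protocol Section 12: "This combined set will serve as the basis for all analyses detailed in this section". Demographics (12.3), discontinuation tables (12.5) and safety (12.6) all fall within that section.
- SAP Section 1 opens with the primary and secondary effectiveness objectives and ends: "all planned analyses will be performed on the combined set of data".
- SAP Section 2: "This combined set will serve as the basis for all analyses for the primary and secondary effectiveness objectives".

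Protocol Section 12 and SAP Section 2 set the same entry criterion for C009 subjects: best corrected acuity of 20/20 or better in each eye at the baseline visit.

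The safety set in Protocol 12.2.1 is "all subjects/eyes exposed to any study lenses evaluated in this study", and SAP 2.1 uses the same words. The SAP's full analysis set (2.2) is "the set of all randomized subjects who are exposed to any study lenses evaluated in this study", with the further condition of a post-baseline acuity measurement. Under SAP Section 3, demographic and lens-history summaries "will be presented by lens group and overall for the safety, full, and per protocol analysis sets".

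Protocol 12.6 and SAP 5.2 state that safety carries no hypotheses.

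**The concern.** Read literally, Protocol Section 12 puts the safety tables on the pooled data, while SAP Section 2 mentions only the effectiveness objectives. SAP Section 1 can be read either way.

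The set definitions do not obviously settle it. In the pooling sentence, "Data from a subset of subjects in the CLL949-C009 study will be combined with data from this study", the phrase *this study* must mean C018 as distinct from C009. The safety set and the full analysis set then use the same phrase, yet the full analysis set has to admit C009 subjects if the effectiveness tests are to be pooled. A programmer could fairly ask which meaning applies to safety.

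Safety is one of the study's stated purposes and is reported descriptively, so set membership fixes who is counted in the adverse event and biomicroscopy tables. Two structural effects would follow:

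- If safety is C018 alone and the full analysis set is pooled, the full analysis set is not a subset of the safety set and could be larger.
- If safety is pooled, the acuity criterion would leave out some C009 subjects who wore the lenses, although the definition speaks of all exposed subjects.

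**Working it through.** **1. Are the scope sentences incompatible?**

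| Place | Reach stated | Safety excluded? |
|---|---|---|
| Protocol 12 | All analyses in Section 12 | No; 12.6 lies inside it |
| SAP 1 | All planned analyses, after a clause naming the effectiveness objectives | No |
| SAP 2 | Analyses for the primary and secondary effectiveness objectives | No; it does not say *only* |

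All three can hold together if everything is pooled. SAP 2 suggests a narrower reach but does not impose one. This is a difference of scope, not a contradiction.

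**2. Do the set definitions force a conflict?** The wording concerns exposure to lenses evaluated in this study. That last phrase can attach to the lenses, in which case it identifies the products and not whose subjects count. A C009 subject who wore one of those lenses then fits the full analysis set, and the apparent double meaning goes. This does not decide safety membership, but it removes the main support for a conflict beyond the scope sentences themselves.

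**3. Where is text hidden?** Redactions follow the C009 criterion in Protocol 12, the safety definitions in Protocol 12.2.1 (in mid-sentence) and SAP 2.1, and the full analysis set in SAP 2.2. In Protocol 12.2.2 the noun after *this* is removed. Any introduction to SAP Section 5 is also not visible. Membership may already be stated in these places.

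**4. What depends on the answer?** The primary and secondary tests are pooled on every reading, and the primary model in Protocol 12.4.1.2 has a random term for protocol. No figure for power, sample size or margin rests on the safety set, so there is no stated figure to reproduce.

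**5. How far could descriptive rates move?** Inputs: 152 test and 76 control subjects planned for randomization (SAP Table 1-1). The number of C009 subjects is not visible, so *m* retained test-lens subjects is an assumption. One event is 1/n. The one-sided 95% upper bound with zero events is 1 − 0.05^(1/n).

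| Group | n | One event | Zero-event bound |
|---|---|---|---|
| Control, C018 alone | 76 | 0.66% × 2 = 1.32% | 3.87% |
| Test, C018 alone | 152 | 0.66% | 1.95% |
| Test, *m* = 50 | 202 | 0.50% | 1.47% |
| Test, *m* = 100 | 252 | 0.40% | 1.18% |
| Test, *m* = 150 | 302 | 0.33% | 0.99% |

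Across this range the rate for one event moves by at most 0.66 − 0.33 = 0.33 percentage points, and the bound by 1.95 − 0.99 = 0.96 points.

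These figures show scale only. The counts are approximate numbers randomized, not numbers exposed. SAP 5.3.1 and 5.3.2 report ocular adverse events and biomicroscopy by eye. SAP 5.3.3 plans only counts and listings for device deficiencies. The visible plan computes no zero-event bound.

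**The case for a change.** The strongest case for a change is that redaction cannot explain the mismatch: all three scope sentences are fully visible, and they differ. No visible sentence says whether the SAP's wording departs from the protocol on purpose. The repair would cost a few words, and making it before unmasking would prevent anyone from choosing the safety denominator once events are known. The two structural effects, on the nesting of the sets and on C009 subjects left out by the acuity criterion, are also real.

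Some of this stands. The wording does differ, and one consistent statement would be tidier. Any demographic or safety table should say which studies it covers, and a pooled safety table should say how the acuity criterion was applied.

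The argument about a late choice of denominator carries less weight here. There is no safety test to steer, and SAP 5.3.1 provides individual listings of adverse events. Sets that do not nest are a labelling matter when one is pooled and the other is not.

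**Conclusion.** No change to the plan follows. The scope of the pool is worded unevenly between Protocol Section 12 and the SAP, but the sentences can be reconciled, and the missing detail may lie in redacted text.

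What is open is which subjects or eyes enter the descriptive safety, demographic and discontinuation summaries. C018 alone and the pooled set would each give a sound summary if labelled. The primary and secondary noninferiority conclusions are the same either way.

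The size of the effect cannot be fixed from the documents, because the number of C009 subjects is not visible. Under the assumed 50 to 150 added test-lens subjects, the rate for a single event would fall from 0.66% to between 0.50% and 0.33%.

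The conclusion rests on two conditions: safety stays descriptive, as both documents state, and the analysts settle membership and label the tables by study, as they must in order to program them.

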2.1 Safety Analysis Set

Safety analyses will be conducted using the safety analysis set on a treatment-emergent basis. As such, the safety analysis set will include all subjects/eyes exposed to any study lenses evaluated in this study. [REDACTED]

[REDACTED] For treatment-emergent safety analyses, subjects/eyes will be categorized under the actual study lenses exposed.

2.2 Full Analysis Set

The full analysis set (FAS) is the set of all randomized subjects who are exposed to any study lenses evaluated in this study, and who have at least one post-baseline (post-Dispense) CLCDVA. [REDACTED]

2.3 Per Protocol Analysis Set

The per protocol (PP) analysis set is a subset of FAS and excludes all data/subjects that have met any of the critical deviation or evaluability criteria identified in the Deviations and Evaluability Plan (DEP).

3 Subject Characteristics and Study Conduct Summaries

Demographic information (age, sex, ethnicity, and race), recent lens-wearing experience (wear modality, wear success), and habitual lens information will be presented by lens group and overall for the safety, full, and per protocol analysis sets.

Baseline data will also be summarized by lens group and overall on the safety, full and per protocol analysis sets.

[REDACTED]

- [REDACTED]
- [REDACTED]
- [REDACTED]
- [REDACTED]
- [REDACTED]
- [REDACTED]
- [REDACTED]
- [REDACTED]

4 Effectiveness Analysis Strategy

[REDACTED]

[REDACTED]

[REDACTED] Primary inference will be done on the PP analysis set. [REDACTED]

[REDACTED]

[REDACTED]

[REDACTED]

[REDACTED]

[REDACTED]

[REDACTED]

[REDACTED]

[REDACTED].

All data obtained in evaluable subjects/eyes will be included in the analysis. No imputation for missing values will be carried out for the effectiveness analyses.

For all planned inferential analyses, alternative models/methods may be considered if convergence cannot be achieved.

[figure not shown]

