3 PROTOCOL SUMMARY

This will be a prospective, randomized [REDACTED] controlled, double-masked, parallel-group clinical study.

Approximately 14-17 sites in the US will enroll approximately 252 subjects. [REDACTED] Subjects will be expected to attend 4 office visits: Screening / Baseline / Dispense, Week 1 Follow-up, Month 1 Follow-up, and Month 3 Follow-up/Exit. The total expected duration of participation for each subject is approximately 3 months in this daily wear clinical study. Accounting for both screen failure and dropout rates, approximately 152 subjects will be assigned to wear the test lenses and 76 subjects will be assigned to wear the control lenses, [REDACTED]

[REDACTED]

Subjects and the study personnel conducting the study evaluations will be masked to treatment. Subjects who meet the inclusion and exclusion criteria will be randomized to wear either the test contact lenses [REDACTED] in both eyes or the control contact lenses (Biofinity) in both eyes for 3 months of daily wear exposure.

[REDACTED]

[REDACTED]

At the Screening / Baseline / Dispense Visit, study lenses will be dispensed to qualified subjects [REDACTED]

All study lenses will be worn for at least 5 days per week and 8 hours per day in a daily wear modality (eg, will not be worn while sleeping).

[Redacted]

[Redacted]

[Redacted]. Regardless of whether the subject is randomized to the test or the control group, CLEAR CARE® Cleaning & Disinfecting Solution (CLEAR CARE) must be used for cleaning and disinfection.

[Redacted]

[Redacted]

[Redacted]

Investigational product type	Medical Device
Study type	Interventional
Investigational products	Test Product: [Redacted] soft contact lens Control Product: Biofinity soft contact lens
Purpose and rationale	The purpose of this clinical study is to demonstrate the safety and performance of the investigational [Redacted] soft contact lens compared to the commercially available Biofinity soft contact lens, when worn in a daily wear modality, by assessing visual acuity as the primary endpoint.
Objective(s)	The primary effectiveness objective is to demonstrate noninferiority [Redacted] compared to Biofinity in CLCDVA at Week 1 Follow-up.

	
 █ [REDACTED] █ [REDACTED] █ [REDACTED] █ [REDACTED] █ [REDACTED] 
Safety
 
 • AEs • Biomicroscopy • Device deficiencies

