12.1 Subject Evaluability

Final subject evaluability must be determined prior to breaking the code for masked treatment (lens) assignment and locking the database, based upon the Deviations and Evaluability Plan (DEP).

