4.3 Statistical Methods for Effectiveness Analyses

4.3.1 Primary Effectiveness Analyses

A mixed effects repeated measures model will be utilized to test these hypotheses. 

 Lens difference (Mercury minus Biofinity) and the

corresponding two-sided 95% CI will be computed for Week 1 Follow-up. Noninferiority in CLCDVA will be declared if the upper confidence limit is less than 0.10.

[REDACTED]

[REDACTED]

[REDACTED]

[REDACTED]

- [REDACTED]
- [REDACTED]
- [REDACTED]

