4.3.2 Secondary Effectiveness Analyses

[REDACTED]

[REDACTED]

[REDACTED]

[REDACTED]

[figure not shown]

[Redacted line]

[Redacted line]

[Redacted]. From the two-sided 95% CI on the lens difference (Mercury minus Biofinity), noninferiority in proportion of subjects achieving 20/20 or better in CLCDVA in both eyes will be declared if the lower confidence limit is greater than -0.10.

[Large redacted area]

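### Primary inference is on the per-protocol set and no visible text requires the FAS to agree; if exclusions are related to vision, the 20/20 responder test can pass too easily

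*SAP*

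**What the plan says.** SAP section 4 (Effectiveness Analysis Strategy) states: "Primary inference will be done on the PP analysis set". The text on both sides of that sentence is redacted, as is the body of Protocol 12.4 before its subsections.

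SAP 2.3 says the PP set "is a subset of FAS and excludes all data/subjects that have met any of the critical deviation or evaluability criteria identified in the" DEP. The DEP is a separate document and is not supplied. SAP 2.2 defines the FAS as randomised, exposed subjects "who have at least one post-baseline (post-Dispense) CLCDVA". In the visible text the FAS is used for demographic and baseline summaries.

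Each declaration rule asks for one confidence limit. For the primary endpoint (SAP 4.3.1): "Noninferiority in CLCDVA will be declared if the upper confidence limit is less than 0.10". For the 20/20 responder endpoint (SAP 4.3.2), noninferiority "will be declared if the lower confidence limit is greater than -0.10".

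Protocol 12.1 sets the timing of exclusions: "Final subject evaluability must be determined prior to breaking the code for masked treatment (lens) assignment and locking the database". Protocol 12.5 and SAP 4 rule out imputation for the effectiveness analyses.

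**The concern.** The PP set is selected after randomisation. If the reasons for exclusion are linked to how well a subject sees, the arms that remain are no longer the arms that were randomised. Such a link is plausible here. The protocol summary sets a wear requirement ("All study lenses will be worn for at least 5 days per week and 8 hours per day"), and someone who sees poorly through a lens may wear it less.

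Masked evaluability prevents knowing selection. It does not stop an exclusion criterion from picking out poor-vision subjects, and it does not stop one lens from producing more of them. Even a criterion that removes the same share of failures from each arm favours the worse lens, because that lens has more failures to lose.

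At stake is the formal noninferiority claim on the 20/20 responder proportion: a lens at the 10-point margin could pass more often than the nominal 2.5%.

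**Working it through.** **Inputs from the documents.** Responder margin -0.10; two-sided 95% CI; 2:1 allocation; about 228 randomised (152:76); target of 192 completers (128:64); no imputation; a subset of CLL949-C009 added for the effectiveness analyses, of unreadable size.

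**The plan's own figure.** The implied loss from randomised to completed is 1 - 192/228 = 15.8%. Inflating 192 by an assumed 15% gives 192/0.85 = 226, close to 228. The planned dropout rate, success rates and power are not readable, so this checks consistency only.

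**Assumptions.**
- 144:72 subjects with Week 1 data (152:76 less 5%: 144.4 and 72.2).
- Control success of 90% or 95%.
- True difference of exactly -10 points, so test failure rates are 20% and 15%.
- Newcombe interval, because the planned CI method is redacted: L = d - sqrt[(pT - lT)^2 + (uC - pC)^2], with lT and uC Wilson limits.
- Every excluded subject has Week 1 acuity and so would count in the FAS.

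**1. Expected shift in the difference.** Exclusions equal to 2% or 4% of the test arm (about 2.9 or 5.8 of 144 subjects), all failures, are a fraction e of test failures. With control 90%, e = 2/20 = 10% or 4/20 = 20%. With control 95%, e = 2/15 = 13.3% or 4/15 = 26.7%. At the largest e:
- Control 95%, test-arm failures only: 0.85/0.96 - 0.95 = 0.885 - 0.950 = -6.5 points.
- Control 95%, same fraction in both arms: control becomes 0.95/(0.95 + 0.05 x 0.733) = 0.963; difference = 0.885 - 0.963 = -7.7 points.
- Control 90%, test-arm failures only: 0.80/0.96 - 0.90 = -6.7 points.
- Control 90%, same fraction in both arms: 0.833 - 0.90/0.98 = 0.833 - 0.918 = -8.5 points.

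The true difference is -10 points in every case.

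**2. False-pass rate.** 200,000 simulated trials per scenario, each failure excluded independently with probability e:

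| Control success | Failures removed (e) | FAS | PP, same e in both arms | PP, test arm only |
|---|---|---|---|---|
| 90% | 10% | 2.8-2.9% | about 4% | 6.1% |
| 90% | 20% | 2.8-2.9% | 5.9% | 11.9% |
| 95% | 13.3% | 2.8-2.9% | about 5% | 7.5% |
| 95% | 26.7% | 2.8-2.9% | 10.1% | 17.0% |

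If both sets must pass, the rate cannot exceed the FAS rate of 2.8-2.9%.

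**3. Size of the pooled set.** At double size (an illustration of C009 adding as many subjects), the test-arm-only rates are 7.7% and 18.7% (control 90%), and 10.4% and 29.1% (control 95%). For a fixed excluded fraction the bias stays the same while the interval narrows.

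**4. Single data sets, 128:64.**
- Newcombe: PP 122/128 vs 61/64 has d = 0 and lower limit -6.0 points (pass). Restoring five excluded test failures, 122/133 vs 61/64, gives -10.3 (fail).
- Wald, L = d - 1.96 x sqrt[pT(1-pT)/nT + pC(1-pC)/nC]: 115/128 vs 61/64 gives -0.0547 - 1.96 x 0.0376 = -0.128 (fail). Without four test failures, 115/124 vs 61/64 gives -0.0257 - 1.96 x 0.0352 = -0.095 (pass).
- At double size the first example no longer flips. Against 122/128, restoring five failures (244/261) gives -6.3 and restoring ten (244/266) gives -8.3. Both pass.

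**5. Primary endpoint.** If 4% of subjects, each 0.30 logMAR worse, are removed, the mean moves by 0.04 x 0.30 = 0.012. At 128:64, with assumed SD 0.06-0.12 and between-eye correlation 0.5-0.8, the 95% half-width is 0.016-0.034. At zero true difference, 0.012 + 0.034 = 0.046, well inside 0.10.

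**The case against.** The strongest objection is redaction. A reader might infer that the plan decides noninferiority on the PP set alone. The documents do not support that: hidden text beside the quoted sentence, in Protocol 12.4 or in SAP 4.3 could require the FAS to agree, and the visible sentence does not exclude it. This objection stands, and the point is limited to what is visible. If the hidden text only calls the FAS supportive, the decision still rests on PP.

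A reader might also infer that the test lens will cause its own exclusions. That is not shown either. The DEP is unseen, and the wear requirement is an instruction to subjects, with no visible text making a shortfall a critical deviation. Exclusions unrelated to outcome would not inflate the error rate. The figures show what happens if some exclusions are linked to vision.

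Three further objections hold in part:
- Removing only test-arm failures is a one-sided worst case. Applying the same fraction to both arms roughly halves the largest figures at 144:72 (11.9% to 5.9%, 17.0% to 10.1%), but they stay above 2.5%.
- The single-data-set examples omit the C009 subjects, and at double size the Newcombe example no longer flips. The pooled size is unknown, so no specific number of exclusions can be called decisive.
- That the quoted sentence governs the secondary test is the natural reading of a general strategy section, but it is not spelled out.

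Finally, FAS agreement does not by itself cover subjects who stop before Week 1. With no imputation they may have no responder value in the FAS either. This is correct, and the fix has to deal with it.

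**Conclusion.** The concern holds as a conditional one. Primary inference is on a set formed after randomisation, and no visible text makes the FAS part of the decision. If exclusions are related to vision, the false-pass rate on the 20/20 test rises from 2.8-2.9% to 4-10% with the same fraction of failures removed in both arms, and to 6-17% with test-arm failures only. These ranges rest on a true difference of -10 points, control success of 90-95%, 144:72 subjects, a Newcombe interval and removal of 10-27% of failures, none of which the readable plan fixes except the margin.

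It would be wrong to extend this to the primary endpoint: the mean acuity comparison has ample room inside its margin. Masked evaluability is a real safeguard against deliberate selection, but it does not address this mechanism.

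**What to change.** In SAP 4 and Protocol 12.4, state (or confirm, if the redacted text already does so):

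> Noninferiority will be declared only if the confidence limit clears the margin in both the PP set and the FAS, using the same method. In the FAS responder analysis, subjects without Week 1 CLCDVA are counted by a stated rule (for example as non-responders, with the observed-data result also shown).

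The work is a wording change and a second run of the same code on a set the plan already defines. With random exclusions of 5% and 10% at 144:72, power on the secondary test falls from 67.9% to 65.9% and from 66.1% to 63.7% at 90% success, and from 90.5% to 89.8% and from 89.7% to 88.8% at 95% success. A second run gave losses of 0.7-2.6 points, so about 1-2.5 points is a fair summary. The loss is under 1 point at double size and essentially nil on the primary endpoint. Counting subjects without Week 1 data as non-responders could cost more, depending on how many there are, which the documents do not say.
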